However, due to the only recent identification of this process, there has not yet been an attempt to stimulate the pharyngeal muscles with noradrenergic drugs in sleeping humans. Now, more than ever, the stage has been set for stimulating the pharyngeal muscles across both NREM and REM sleep.

II. SPECIFIC AIMS

To determine the effect of noradrenergic, antimuscarinic and potassium channel blocker drugs on pharyngeal muscle activity during sleep. We hypothesize that existing drugs with these neurotransmitter profiles could (partially) restore pharyngeal muscle activity in humans during sleep.

Specifically, we will test this hypothesis by assessing;

The effect of the combination of atomoxetine (a norepinephrine reuptake inhibitor) plus fesoterodine (a newer, extended-release antimuscarinic drug) on OSA severity (DAW1033B2). Fesoterodine is an extended-release antimuscarinic with less reported side effects compared to oxybutynin. Fesoterodine could be a good candidate for a long-term therapy in subjects with OSA and the data collected in this pilot study will help to design a long-term clinical trial to test the efficacy of this association for the treatment of OSA.

1.

III. SUBJECT SELECTION

We will recruit a group of subjects with OSA. These subjects will be recruited from the community and be between 21-65 years old. The purpose of studying patients with OSA is to determine what effect this drugs will have on improving the patient's OSA severity.

- a) **Obstructive Sleep Apnea Patients (n= 15):** Patients with OSA will be recruited from our clinical sleep laboratory at Brigham and Women's Hospital, as well as from our existing database of OSA patients. These individuals will be otherwise healthy (except for well-controlled hypertension; defined as systolic blood pressure <140 mmHg and diastolic <90 mmHg) with no active medical problems and on no medication that could affect respiration or muscle control. All will be 21-65 years of age. Both men and women will have an apnea-hypopnea index (AHI) >15 events/hr during supine NREM sleep. These individuals will be recruited to encompass a large range of AHI's (from 10 to >60/hour).

Exclusion criteria:

- Any medical condition other than well controlled hypertension, GERD, hyperlipidemia.
- Any medication known to influence breathing, sleep/arousal or muscle physiology.
- Claustrophobia.
- Inability to sleep supine.

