Subjects who respond will be given a thorough review of the risks, discomforts, potential benefits to the study and their expected involvement using a prepared script approved by our Institutional Review Board. Subjects will be given a copy of the informed consent and allowed a minimum of 24 hours to review the information and make a decision on study participation. During this time, the subject will have the opportunity to discuss the research with his/her primary care physician or clinician. The study investigators will be available to answer any questions should any arise. Informed consent will be obtained by the Principal Investigator or an experienced co-investigator prior to participation in the study. The opportunity to talk to a licensed MD (who is readily available at the time of consent, and available overnight at the hospital) will be offered in each case. Subjects will have more than 24 hours to consider participating in the study. Any consent issues / problems will be reported to the PHRC in real time rather than waiting to report at the time of Continuing Review

Inclusion and exclusion criteria will be carefully assessed prior to enrollment. Assuming subjects meet the inclusion criteria, they will begin the protocol by scheduling their overnight studies in the clinical/physiology laboratories. Subjects will be informed that they may withdraw from the study at any point, with no impact on their ongoing care. We have not previously had difficulty enrolling participants into similar studies performed in our laboratory.

If the data collected will be considered insufficient by the PI or by the co-investigators, the subject will be asked to repeat the whole study or a part of it without signing a new informed consent form.

V. STUDY PROCEDURES

Protocol:

PARTNERS HUMAN RESEARCH COMMITTEE

DETAILED PROTOCOL

Version: March 8, 2017

Two overnight sleep studies will be performed approximately 1 week apart: a placebo night and a atomoxetine-plus-fesoterodine (DAW1033B2) night, in double-blinded randomized control design. For each night, the subjects will arrive at the sleep laboratory at approximately 7:00pm. A physician will perform a comprehensive physical and medical history. The placebo or atomoxetine-plus-fesoterodine (80+4mg) will be administered 30 minutes before lights out.

Measurements and equipment:

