1. The equipment used for assessing sleep (paste on electrodes) is standard and poses no risk. The electrodes may be mildly uncomfortable and could cause some sleep interruption. Thus subjects may feel somewhat tired the day following this study.

**PARTNERS HUMAN RESEARCH COMMITTEE
DETAILED PROTOCOL**

Version: March 8, 2017

2. Atomoxetine: Side effects include alopecia, dry mouth, tiredness, irritability, nausea, decreased appetite, constipation, dizziness, sweating, dysuria, sexual problems, decreased libido, urinary retention or hesitancy, increased obsessive behavior, weight changes, slowed growth in children, palpitations, increases in heart rate and blood pressure.
3. Fesoterodine: the most common side effects of fesoterodine 4 mg extended release in previous clinical trials were dry mouth and constipation. Less frequent side effects were abdominal pain, dry eyes, dyspepsia and urinary retention.

VIII. POTENTIAL BENEFITS

Although it is unlikely that there will be any direct physical benefit to the subjects from participating in this study, we will make known to each subject, if requested, some of the information we have gathered from this physiologic testing. This study provides a unique opportunity to gain insight into the specific mechanisms by which these novel drugs may improve upper airway muscle function. The results may, in the future, lead to improved strategies for the treatment of sleep apnea. However, if previously unknown abnormalities of sleep and breathing are encountered, this information will be passed onto the subject. Results can be forwarded to the primary care physician or clinician at the request of the subject.

IX. MONITORING AND QUALITY ASSURANCE

We will follow the Data and Safety Monitoring Plan included as an attachment. As this study is a physiological investigation and not clinical trial, a formal Data and Safety Monitoring Board will not be implemented. The PI will be responsible for monitoring safety and quality assurance. Additionally, the ongoing results, problems, and limitations of the study will be presented on a regular basis to the investigators in the Division of Sleep Medicine. Any adverse events will be promptly reported to the Human Research Committee for review according to HRC guidelines.

Adequacy of Protection Against Risks

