All of our laboratory personnel involved in the research of human subjects have completed the required institutional program for education in the protection of human research participants and their confidentiality. The institutional educational program consists of the review of regulatory and informational documents pertaining to human-subject research, passing a test demonstrating knowledge of the ethical principles and regulations governing human-subject research and signing a statement of commitment to the protection of human subjects.

All electronic data will be stored on secure computers under password protection with no access allowed to individuals outside of our research team. All paper data will be stored under lock and key with access only given to the study staff.

Protection Against Risks

PARTNERS HUMAN RESEARCH COMMITTEE DETAILED PROTOCOL

Version: March 8, 2017

We believe that all possible safeguards are in place to minimize the risk. However, several steps will be taken to insure patient comfort and safety. We will work with our IRB to come up with a safety monitoring plan to minimize risk and discomfort. This will include:

- Reporting any complications of our studies immediately to the IRB.
- Appoint a safety officer ([name]) who will work with our physicians and technicians to maximize safety and comfort.
- Our study coordinator will call each subject 2-3 weeks after the study to determine if any problems resulted from the study.

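### The supplied text schedules only one post-dose enquiry about side effects, a call 2-3 weeks after the study; a blinded checklist on the morning after each night would be a cheap improvement

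*Combined protocol and SAP*

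**What the plan says.** Section V (Protocol) sets out a two-period crossover, "in double-blinded randomized control design": "Two overnight sleep studies will be performed approximately 1 week apart", one on placebo and one on atomoxetine plus fesoterodine. For each night the text runs from arrival at about 7:00pm, to "A physician will perform a comprehensive physical and medical history", to the study medication, which "will be administered 30 minutes before lights out". The measurements that follow are polysomnography. No symptom question is listed for the night or the next morning.

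Section VII names the effects to expect. For atomoxetine: "Side effects include alopecia, dry mouth, tiredness, irritability, nausea, decreased appetite, constipation, dizziness, sweating, dysuria", among others. For fesoterodine: "the most common side effects of fesoterodine 4 mg extended release in previous clinical trials were dry mouth and constipation".

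Section IX (Protection Against Risks) gives the one planned contact after dosing: "Our study coordinator will call each subject 2-3 weeks after the study to determine if any problems resulted from the study". The rest of section IX covers prompt reporting to the review committee, monthly and as-needed meetings, follow-up by the safety officer of subjects with problems, and classification of events by seriousness, expectedness and relation to the study. It also refers to a Data and Safety Monitoring Plan as an attachment, which is not among the documents supplied.

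Section VI contains no summary of adverse events. Section II gives tolerability as part of the reason for the drug choice, "Fesoterodine is an extended-release antimuscarinic with less reported side effects compared to oxybutynin", and says the pilot data will help design a long-term trial.

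**The concern.** Each subject is exposed twice, once to drug and once to placebo, about a week apart. To be useful, a side effect has to be noticed and then placed on the right night. The plan as supplied relies on one late call, described as being about problems from the study as a whole rather than from each night.

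Mild effects such as dry mouth, nausea or dizziness are the ones a subject may not volunteer. Asked weeks later, the subject may have forgotten them or may not know which night they followed. A subject with a problem after night 2 who does not report it unprompted is not routinely asked about it until the call. At stake are early detection of problems and the tolerability information available to whoever designs the long-term trial.

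**Working it through.** The plan states no figure on this point, so there is none to reproduce. The check is date arithmetic on two stated intervals, followed by a reading of the other safety provisions.

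**Inputs**
- Gap between nights: about 1 week, taken as 7 days (section V).
- Call: 2-3 weeks after the study, taken as 14-21 days (section IX). The text does not define the end of the study for a subject; it is first read as the second night.

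**1. Delay from each night to the call**
- Night 2: 14 to 21 days.
- Night 1: 14 + 7 = 21 days, to 21 + 7 = 28 days.

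**2. Alternative reading: a call after each night**
- The night-1 call would fall 14 - 7 = 7 to 21 - 7 = 14 days after night 2. Both exposures would still precede the first call.

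**3. Does the physician's history fill the gap?**
- It is described after arrival and before dosing, so it cannot record that night's effects.
- At night 2 it comes about 7 days after night 1. Anything found then precedes the second dose and so belongs to night 1. It is not, however, described as an adverse event enquiry.
- Night 2 has no later visit. Its first scheduled question is the call, at 14-21 days.

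**4. Do the other provisions ask the subject anything?**
- Reporting, meetings, safety-officer calls and classification in section IX all act on events already known.
- The classification described does not include the study night or treatment period.
- EKG and continuous oximetry in section V may show overt acute events. They do not detect dry mouth, nausea or constipation.

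**5. Do the delays differ between drug and placebo?**
Assume half the subjects receive drug first; the plan says randomized but gives no ratio. Each condition then occupies night 1 in half the subjects and night 2 in the other half.
- Call only: mean delay for either condition is (14 + 21)/2 = 17.5 to (21 + 28)/2 = 24.5 days.
- History counted as the night-1 enquiry: (7 + 14)/2 = 10.5 to (7 + 21)/2 = 14 days.

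Under each reading the mean is the same for drug and placebo.

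**6. With a morning-after question**
The delay becomes less than about 1 day for each night. The sample size is unaffected: 12 completers with about 20% failure still gives 12/0.80 = 15.

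The number of events lost cannot be calculated. The documents give neither an event rate for these subjects nor a figure for recall.

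**The case against.** The strongest reply is that the absence is not proven. The monitoring plan is an attachment that was not supplied, and the list in section IX containing the call is introduced as what the arrangements will include, not as a complete list. This stands, and the point is limited to the supplied text.

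Second, no side-effect comparison is planned. The aim concerns OSA severity, the sample size rests on AHI, the long-term trial is described as testing efficacy, and there is no oxybutynin arm. This also stands: no planned analysis is damaged. What can be lost is tolerability information that the pilot could collect at almost no cost.

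Third, subjects sleep in a laboratory under recording, complications are to be reported immediately, and nothing stops the coordinator from asking for dates during the call. These are real routes for observed or volunteered problems. They are not systematic enquiry, and the plan does not say that dates or nights will be asked for.

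A reader might infer that the delays bias the drug-placebo contrast through treatment order, because night 1 could be asked about at 7 days and night 2 only at 14-21, a two- to three-fold difference. The documents do not support this. The ratio holds only if the pre-dose history counts as an enquiry; if it does not, night 1 has the longer delay. Either way, randomized order spreads the delays over both conditions. Chance imbalance in order among 12 completers is possible, but no bias is shown.

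**Conclusion.** The point holds as a cheap improvement, not as a defect in the efficacy analysis. In the supplied text, the first scheduled question about night-2 effects comes 14-21 days after that night. Night-1 effects are asked about at 21-28 days, unless the history before the second dose happens to bring them out at about 7. Mild effects may be missed or assigned to the wrong night, and problems after night 2 that are not volunteered may go unnoticed for weeks.

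This rests on reading the end of the study as the second night, on a 7-day gap, and on the unseen attachment adding no earlier enquiry. The AHI comparison is unaffected. A reader should not infer that side-effect counts would favour drug or placebo, or that a known number of events would be lost; the documents support neither.

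**What to change.** In sections V and IX, add a short symptom checklist covering the effects listed in section VII. Staff already present ask every subject the same questions on the morning after each night, before the subject leaves and while all remain blinded. Record the answers against that night. In section VI, add a descriptive table of counts by treatment, without a test. Keep the 2-3 week call for late events.

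If the attached Data and Safety Monitoring Plan already provides this, a cross-reference in sections V and IX is enough.

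The cost is one form and one table, with no change to sample size, dosing or the AHI analysis. The one drawback is that prompted questions raise counts on both nights, so the placebo-night count should always be shown beside the drug-night count.
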